## **Counselor Measures**

**Counselor Background Form (CBF):** The CBF was developed for this study and assesses the demographics and work/training histories of each participating counselor. Additionally, for this study, we have added questions on counselor's experience with medication assisted treatment. *Administered at baseline only.*

**Counselor Satisfaction Form:** The Counselor Satisfaction Form was developed for this study and assesses the extent to which counselor participants perceived the intervention to be helpful and useful. It contains both closed- and open-ended questions in order to obtain information that will help us further refine the intervention for dissemination. *Administered at 6 months only.*

**Counselor Shared Decision Making Questionnaire (SDM-Q):** The Shared Decision Making Questionnaire (SDM-Q counselor version; Simon et al., 2006) is a validated 9-item questionnaire that measures the process of shared decision making between clinicians and patients. We adapted this measure to apply to substance abuse treatment decision making. This version of the questionnaire measures shared decision making from the clinician's perspective. *Administered at baseline and 6-months.*

**Counselor Evidence-Based Practices Questionnaire:** The Evidence-Based Practices Questionnaire (Abraham et al., 2009). measures counselors' attitudes and familiarity with a range of evidence-based practices, such as MAT, CBT, and MET. *Administered at baseline and 6 months.*

**Counselor Fidelity Checklist:** The Counselor Fidelity Checklist will indicate the content areas that were covered in treatment during the intervention period. It will measure counselors' adherence to their assigned intervention, and it will help detect any between-condition contamination. *Ongoing; completed after each study treatment session.*

**8. Describe characteristics of the subject population, such as their anticipated number, age ranges, sex, ethnic background, and health status. The study should employ a study design with gender and race representation appropriate to the purpose of the research. Strong justification must be provided for exclusion of broad population groups. Identify the criteria for inclusion or exclusion. Explain the rationale for the use of vulnerable populations as research subjects (i.e., prisoners, pregnant women, disabled persons, drug users, children).**

Research participants will be patients currently receiving treatment at one of our participating inpatient or outpatient substance abuse treatment sites. We expect that 350 participants will enroll in the study. We will not exclude any potential participant based on race or gender, and members of gender and minority groups, the elderly, and disabled will be included in the research in the same proportion as they are represented in the populations of patients served at the participating treatment sites. We anticipate that the demographic characteristics associated with the client participants will be similar to the characteristics of the clients we have recruited in the Philadelphia area in the past; clients are, on average, 30% female, 36% Black, 51% White, 13% other minorities, and 15% Hispanic. Elderly subjects and those with medical problems will be included in the research as long as they are able to give competent, informed consent and understand the content of the research instruments. Participants with disabilities will be accommodated. We will monitor gender and minority representation to ensure that it is representative of the target population, and we will over-sample any gender and racial groups that are significantly under-represented.

**9. Describe plans for recruitment of subjects, including advertisement and posters and the consent procedures to be followed, including the circumstances under which consent will be sought and obtained, who will seek it, the nature of the information to be provided to prospective subjects and the methods of documenting consent.**

Counselor Recruitment

We will travel to the inpatient and outpatient substance abuse treatment sites in order to present the study and recruit counselor participants. After presenting the study, interested counselors can schedule a time with research staff to consent into the study. At this scheduled time, research staff will obtain written informed consent and will then administer an assessment battery as part of the Baseline Interview. Research staff will only work with treatment sites whose administrators agree that they will not impose any negative consequences on counselors who choose not to participate in the study. We then will randomly assign counselors to the toolkit (TK) or treatment-as-usual (TAU) group, and counselor participants will schedule a time to complete the initial training on their assigned condition. Counselors will be paid \$25 for measures completed at the Baseline Interview, \$75 for the initial training, \$25 for each of the 3 booster trainings, \$20 for each set of 5 fidelity checklists up to \$200, and \$25 for measures completed 6-months post Baseline Interview. Counselors can earn up to \$400 throughout the course of the study.

Client Recruitment

Immediately after a counselor completes training (either TK or TAU), we will work with the counselor to schedule a date within the next two weeks to present the study to patients who are on his or her caseload. On the scheduled day, research staff will travel to the treatment site and will present the study to those patients who attend individual therapy sessions with the counselor. Patients who are interested in the study will be asked to complete a brief verbal screening consent. We will administer the AUDIT; patients who score a 16 or above (criteria for moderate to severe alcohol use disorder) will receive further screening. We will then administer the MINI (modified for DSM-V criteria). Patients must meet criteria for current alcohol SUD (i.e., positively endorse at least 2 of the 11 items on the MINI) and have experienced 6 days of alcohol use in the past 60 days in order to be eligible. To maximize

generalizability and practical relevance of our findings, only patients who are unable to provide valid informed consent will be excluded. We expect to recruit 50 patients.

#### Inclusion and Exclusion Criteria

*Inclusion Criteria:* (a) patient is on the caseload of a participating counselor, (b) patient is 18 years or older, (c) a screening score of at least 16 on the AUDIT, (d) patient meets criteria for a substance use disorder as defined by DSM-V assessed via the MINI Plus 5.0, (i.e., endorsement of at least 2 of the 11 items on the MINI), (e) the patient has enrolled in the treatment program within 4 weeks prior to the date of consent and (f) patient reports 6 days of alcohol use in the past 60 days. Each participant must meet all the inclusion criteria in order to be enrolled in the study.

*Exclusion Criteria:* (a) the patient reports plans to leave the Philadelphia greater metropolitan area within the next 6 months; (b) the patient is not English-speaking; (c) the patient is mandated to attend inpatient treatment (i.e. considered a prisoner), or (d) if the patient is unable to provide valid informed consent by correctly describing the key components of consent to the RA.

Research staff will work with participating counselors to identify patients on their caseload who have enrolled in treatment within the past 4 weeks. Patients who are identified as potential study participants will be asked to complete a screening consent with an RA. We are requesting a waiver of written documentation of consent for the screening process. According to 45 CFR 46.117(c), written documentation may be waived if “the only record linking the subject and the research would be the consent document and the principal risk would be potential harm resulting from breach of confidentiality.” For patients who are found ineligible through the screening process, the screening consent form would be the only written document linking the patient to the research, thus a requirement for written consent would paradoxically be the only real danger to loss of privacy and confidentiality for participants who agree to be screened. We will provide an information sheet (i.e. a screening consent) to patients prior to screening that contains informed consent information, and we will obtain verbal consent that the patient is willing to participate in the screening. For patients who consent to screening, the RA will administer the AUDIT, MINI, and 8-week TLFB to determine if they meet inclusion criteria. Patients who meet the inclusion criteria and are interested in participating will be asked to provide written informed consent. Study research assistants (RAs) will fully explain the study procedures to eligible patients, and will obtain informed consent from those interested in participating.

During the informed consent process, patients will be fully informed of the procedures, the nature of the study conditions, inclusion and exclusion criteria for the study, and the compensation associated with participating in the study. They will be informed that all research data collected in the study will be kept strictly confidential and that we have applied for or obtained an NIH Confidentiality Certificate that will shield the research data from a subpoena or court order. The only exceptions to confidentiality (clearly specified in the consent form) will pertain to information related to medical emergencies, disclosure of current child/elder/dependent abuse or neglect, or imminent risk of death or serious injury to the participant or others. Finally, these individuals will be informed of all known potential risks and benefits of participation, their right to refuse or revoke consent at any time, and the names and phone numbers of responsible individuals they may contact for additional information or to register complaints about study procedures. They will also be asked to complete a brief consent quiz to ensure their understanding of the study requirements, the risk and benefits, and their human subject protections. All items answered incorrectly will be reviewed with the participant to ensure adequate understanding. This process will continue until participants demonstrate at least a 95% understanding of the essential elements of the informed consent document. Potential participants will then be asked if they have any questions and will be asked to sign the informed consent form to document their agreement to participate. They will receive a duplicate copy of the consent form for their records. The original signed consent form will be kept in a locked filing cabinet only accessible to staff working on this study.

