## Data Analysis Plan

**Data Management and Analysis-** All interview and self-report measures will be completed via a web-based data entry program that has been used at TRI and the University of Pennsylvania for the past 5 years. Direct data entry reduces errors that can occur when transferring information from paper forms into electronic files. See our Data Management Plan for data integrity procedures. Prior to performing analyses, standard data screening/cleaning procedures will be applied: re-screening the data for data-entry errors, assessing the extent and pattern of missing data, and checking that appropriate assumptions of normality are met, employing remedial measures when necessary. We will check to confirm that the groups do not differ at baseline on relevant background variables using analyses of variance (ANOVA) for continuous variables and log-linear models for discrete or ordinal responses. The randomization process should minimize the need for the inclusion of covariates to reduce bias in the treatment comparisons. However, relevant covariates will be considered for inclusion in the analyses to improve the precision of estimation of the effects .

**Exploratory Hypothesis 1: Patients in the TK Condition will** participate in shared decision making conversations with their counselors at higher rates than patients randomized to **TAU**. Number of sessions in which patients indicate that their counselors conducted a shared-decision making conversation at the 6-week and 3-month follow-up will be examined. Average number of sessions per patient will be compared at the 6-weeks and 3-month follow-up point. We will calculate effect sizes between conditions using Cohen's d. Quality of shared decision making conversations will be calculated using a subscale of the fidelity checklist. Differences in patient perceived quality will be averaged, and effect sizes will be calculated using Cohen's d.

**Exploratory Hypothesis 2: Patients in the TK will report greater satisfaction and acceptability with their individual sessions than patients randomized to TAU.** Scores on the Patient Satisfaction measure will be averaged and compared between conditions for the assessment at the three-month follow-up point. We will calculate overall Satisfaction rating and Satisfaction with the Referred Services Subscale score. We will calculate effect sizes using Cohen's d.

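### Counselors are randomized and know their arm before their patients are identified, so randomization does not by itself balance the patients, and the SAP's baseline tests are too weak to confirm balance

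*Protocol*

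**What the plan says.** The order of events is in Protocol section 9. After counselors consent and complete baseline measures: "We then will randomly assign counselors to the toolkit (TK) or treatment-as-usual (TAU) group, and counselor participants will schedule a time" for training. Client recruitment follows: "Immediately after a counselor completes training (either TK or TAU), we will work with the counselor to schedule a date" on which the study is presented. The same section adds: "Research staff will work with participating counselors to identify patients on their caseload who have enrolled in treatment within the past 4 weeks". Section 6 confirms that the counselor is the unit allocated and that allocation is within site.

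Two features limit the counselor's part. Research staff "will present the study to those patients who attend individual therapy sessions with the counselor", and "the RA will administer the AUDIT, MINI, and 8-week TLFB to determine if they meet inclusion criteria". Section 9 also says that patients are told about the study conditions before they sign. Neither document describes how patients come to be on a given counselor's caseload, whether every recently admitted caseload patient is approached, or whether approaches are logged.

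The SAP (Data Management and Analysis) says: "We will check to confirm that the groups do not differ at baseline", using ANOVA or log-linear models. It continues: "The randomization process should minimize the need for the inclusion of covariates to reduce bias in the treatment comparisons". It then allows unnamed covariates to be considered, for precision. Hypothesis 3 includes the baseline urine result and other unspecified variables. Hypothesis 4 uses change from baseline. The SAP does not mention that counselors were the unit allocated, and its Missing Data paragraph speaks of patients as randomized.

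**The concern.** When patients are randomized individually, with allocation concealed, a baseline difference can arise only by chance. Here the allocation is known before any patient is identified. Two routes to systematic difference are therefore open: which eligible patients come to the research staff's attention, and which of them agree once the conditions are explained. The AUDIT, MINI and drinking criteria restrict who is eligible. They do not govern who among the eligible is approached or consents.

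The SAP's two safeguards do not cover this. Randomizing counselors balances counselors in expectation, not the patients recruited afterwards. A non-significant baseline test in a study this small says little.

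What is at stake is the effect size. Protocol section 5 sets power aside because the study's purpose, beyond feasibility and acceptability, is to supply effect sizes for sizing a full trial. A biased Cohen's d would be carried directly into that calculation.

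**Working it through.** **Planned size.** Protocol section 4: about 100 screened × 50% = 50 patients; 20 (Year 2) + 30 (Year 3) = 50; 2 × 25 = 50. The figure reproduces. Section 8 gives 350, which conflicts with sections 2, 4 and 9; I use 50. No alpha, power or target effect is stated, so a two-sided 0.05 is assumed throughout.

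**Power of a baseline test.** Two-sample t-test with n = 25 per arm, df = 48 and noncentrality = d × √(n/2) = d × 3.54.

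| True gap (SD) | Noncentrality | Power | Chance of passing as no difference |
|---|---|---|---|
| 0.3 | 1.06 | 18.0% | 82% |
| 0.5 | 1.77 | 41.0% | 59% |
| 0.8 | 2.83 | 79.1% | 21% |

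By the normal approximation, the gap detectable with 80% power is (1.960 + 0.842) × √(2/25) = 0.79 SD. Detecting 0.5 SD with 80% power needs 63 per arm, and 0.3 SD needs 175. For a binary characteristic, 30% against 50% has about 30% power.

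**Clustering.** Design effect = 1 + (m − 1) × ICC. With 50 patients and 31 counselors, m averages 1.6. It is higher if some counselors contribute no patients, as at the site in section 6 that enrolled counselors but no clients. For an assumed ICC of 0.01 to 0.20 and m from 1.6 to 5, power for a 0.5 SD gap (normal approximation, 42.4% unclustered) becomes 42.2% at best and 26.0% at worst. The worst case is 1 + 4 × 0.20 = 1.8, or 50/1.8 = 27.8 effective patients.

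**Effect on Cohen's d.** To first order, bias = gap × correlation of the factor with the outcome. Neither is in the documents, so both are assumed. In a simulation with no true effect, 25 per arm and 40,000 runs:

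| Gap (SD) | Correlation | Mean d, all runs | Mean d, runs passing the baseline test |
|---|---|---|---|
| 0.3 | 0.3 | 0.09 | 0.06 |
| 0.3 | 0.7 | 0.22 | 0.15 |
| 0.5 | 0.3 | 0.15 | 0.10 |
| 0.5 | 0.7 | 0.36 | 0.23 |

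Passing the test reduces the shift but does not remove it.

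**Effect on the next trial.** Patients per arm = 2 × (1.960 + 0.842)² / d² = 15.70/d² (80% power assumed). A true d of 0.30 needs 175 per arm. Read as 0.45, it gives 78; read as 0.15, it gives 698. The 0.15 shift is an illustration, equal to a 0.3 SD gap × a correlation of 0.5.

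**The case against.** A reader might infer that Toolkit counselors choose their most receptive patients. The documents do not say so. Section 9 describes identification by an administrative fact, recent enrollment on the caseload. Staff present the study, and a research assistant applies the criteria. Where the protocol intends counselor referral it says so, for the focus-group clients. What stands is narrower: the counselor, aware of the arm, helps to build the list, and the list is not stated to be complete.

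A reader might also infer that the SAP claims its tests rule out selection bias, or that it has no covariates. Neither is right. The SAP never names selection bias, says only that randomization should reduce the need for covariates, and leaves room for them. Hypotheses 3 and 4 already use baseline information. But apart from baseline urine no covariate is named, and the general provision is for precision, not bias.

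The sizes of the gap and correlation are assumed. The shifts of 0.09 to 0.36 should be seen against a standard error of d of about √(2/25) = 0.28 in a study that calls every hypothesis exploratory. That is fair, but the standard error is at least visible in an interval, whereas a recruitment bias is not.

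Finally, Protocol section 6 shows that recruitment has ended by the funder's decision, so changes to recruitment come too late for this trial. Adjustment also cannot reach factors such as motivation, for which no dedicated measure is listed. Both points stand, and they shape the fix.

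**Conclusion.** The concern holds as a risk of recruitment bias of unknown size and direction. That patients are identified after allocation, with the counselor's help, is explicit in the protocol. That the SAP leans on randomization and on baseline tests is explicit in the SAP.

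The firmest number is the weakness of the tests: about 18% power for a 0.3 SD gap and 41% for 0.5 SD, assuming two-sided 0.05 and the planned 25 per arm. Clustering by counselor, or fewer patients than planned at closure, would lower these. The shift in Cohen's d rests wholly on assumed gaps and correlations and shows only what could go unnoticed. The documents do not support saying that bias occurred, that it favors the Toolkit, or that it affects all six hypotheses equally.

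**What to change.** **(a) SAP wording.** State that allocation was by counselor within site and that patients were not individually randomized. Drop the reliance on randomization to make bias adjustment unnecessary. Replace the confirmatory tests with a descriptive table by arm, with standardized differences.

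**(b) Adjusted estimates.** Report covariate-adjusted effects for Hypotheses 1 to 6, with covariates fixed before analysis: site, AUDIT score, and the baseline value of the outcome or nearest measure where collected:
- Hypothesis 1: baseline client SDM-Q, after checking that it preceded any Toolkit session.
- Hypothesis 2: site and AUDIT only; satisfaction is measured at 3 months only.
- Hypothesis 3: baseline days of use and urine result.
- Hypothesis 4: baseline ASI alcohol score.
- Hypothesis 5: baseline treatment use from the NSMOS.
- Hypothesis 6: a smaller set if few patients initiate.

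**(c) Reporting.** From existing records, give the numbers approached, screened, eligible and consented by arm, and state recruitment bias as a limitation.

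**(d) Follow-on trial only.** Have research assistants screen all recent admissions from the program census, and keep a log.

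The cost is SAP text, retrieval of records and a few degrees of freedom. With patients from two sites, site, AUDIT and one baseline value use three, leaving 48 − 3 = 45 for a continuous outcome. Unmeasured factors remain uncontrolled, so (b) reduces the risk without removing it.

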### Focus Groups

We will recruit Counselor focus group participants from already enrolled counselors assigned to the Toolkit condition. Counselors must have used the Toolkit with at least one of their clients in order to be eligible for the focus group. We will recruit Client focus group participants from counselor referral. We will ask counselors who meet the criteria for our focus group to refer clients who received at least part of the Health Education Toolkit as a part of their care. Clients must have received at least part of the Health Education Toolkit as a part of the care in order to be eligible for the focus group. A member of the TRI research team will speak individually with each prospective focus group participant and explain the procedures of the focus group (types of people participating, activities the group will engage in, and the fact that the group will be audio-recorded). Counselors and clients willing to participate will be scheduled for the appropriate group.

We are requesting a waiver to document informed consent for individuals participating in the focus groups according to **45 CFR 46.117(C)(2)** which states documentation may be waived if “the research presents no more than minimal risk of harm to subjects and involves no procedures for which written consent is normally required outside of the research context.” At the beginning of each focus group meeting, TRI staff will provide a copy of the Focus Group Information Sheet to all participants and will fully explain the focus group procedures. Participants will be asked to provide verbal informed consent to participate, and will be told that they can stop participation at any time by leaving the focus group room.

**10. Discuss whether risks to the subject are ‘minimal’ or ‘greater than minimal.’ List the major risks of subject participation. Describe any possible benefits of subject participation. Are the risks to subjects reasonable in relation to the anticipated benefits to subjects and in relation to the importance of the knowledge that may reasonably be expected to result?**

The risks to subjects enrolled in this study are minimal. There are three anticipated potential risks associated for both counselor and patient participants enrolled in this study.

1. Perception of coercion: It is possible that some participants may feel coerced to participate in the research study. Our previous studies with similar populations indicate that this is a rare event.
2. Discomfort answering research questions and/or providing biological data: Participants may experience mild and transitory psychological discomfort from completing research measures that deal with emotionally laden material or from providing urine samples. The probability of these risks and the magnitude of the anticipated harm are likely to be small. These events have *not* been encountered in any of our previous studies using similar assessments.
3. Harm from Breach of Confidentiality: Participants are at risk for harm as a result of being identified as a study participant or as someone with an alcohol or drug problem. The likelihood of this occurring is small and was not encountered in our previous studies.

*Benefits to participants:* Participants in this study may benefit from receiving an intervention which is designed to educate patients about their treatment options and encourage self-efficacy to access treatment modalities that best address patients’ needs, including alcohol-related MAT. This project will also yield considerable information on behavioral changes associated with the Health Education Toolkit intervention.

*Importance of Knowledge to be Gained:* The aim of this project is to test the impact of a Health Education Toolkit in increasing patient knowledge, increasing treatment modalities accessed, and reducing substance use. The Toolkit series will be designed to communicate pertinent health information to SUD patients in a format that is engaging and easily understood. If this Health Education Toolkit proves to be effective, patients will demonstrate detectable reductions in substance use, higher

engagement rates with supplemental treatments including MAT, and increased knowledge about treatment options.

The risks associated with participating in this study are reasonable given the benefits and importance of knowledge to be gained.

**11. Describe the procedures for protecting against or minimizing any potential risks, including physical, psychological, legal and confidentiality risks, and assess their likely effectiveness. Where appropriate, discuss provisions for insuring necessary medical or professional intervention in the event of adverse events to the subjects and for monitoring the data collected to insure the safety of subjects. Also, where appropriate, describe alternative treatment and procedures that might be advantageous to the subjects.**

1. Perception of coercion: Research staff will be trained to describe the study to eligible counselors and patients, including the risks and benefits, prior to offering an invitation to participate in the study. Research staff will clearly state that the counselor's decision to participate is voluntary and will not affect their employment at the site. Similarly, we will state that a patient's decision to participate is voluntary and that it will not impact the services they receive at their treatment site. Patients will be told that treatment site staff have no vested interest in their participation and will receive no benefit if they choose to participate. All potential participants will be told that if they feel any pressure to participate from any treatment site staff, they can voice this concern to the PI or other TRI research staff, and the PI will discuss this matter with the site's director and/or other appropriate individuals.
2. Discomfort answering research questions and/or providing biological data: Individuals enrolled in any study may experience mild and transitory emotional discomfort when answering the questions posed in interviews and on questionnaires, or providing a urine sample. All participants will be informed about these possible risks before signing the consent form. In order to minimize discomfort with providing a urine sample, the sample will not be collected under observation. The research staff will complete a training regarding monitoring and addressing emotional distress among research participants, as well as an additional training on the urine collection process which will include suggestions for decreasing participant discomfort. Participants will be told that they can choose not to respond to a question that they find upsetting and can withdraw from participation at any time without negative consequence.
3. Harm from Breach of Confidentiality: Data collected in the study will be kept strictly confidential and will not be shared with anyone outside of the research team. The only exceptions to confidentiality, which will be clearly specified in the consent form, will be for information related to medical emergencies, current child abuse or neglect, or imminent risk of death or serious injury to the participant or others. All research materials will be coded with a research number and will contain no other identifying information. Information collected on paper (e.g., consent forms, HIPAA forms, Locator Forms) will be stored in locked filing cabinets at TRI, and computer spreadsheets will be saved in password-protected files. Participants will be assigned a study identification number which will be affixed to all collected data. Linkage between participant identity and identification numbers will be stored in a password protected electronic file available only to the PI and designated research staff. All research instruments will be computerized for this study, and the data will be entered via the Web into a secure server located at the University of Pennsylvania's Data Management Unit. All computers have security codes and password protections to prevent unauthorized access. Efforts to contact participants for telephone check-ins or follow-up appointments will make no mention of the study until it is established that the participant has been reached. Access to participants' telephone numbers, addresses, and other contact information will be limited only to research staff members who need to contact a participant for study purposes.

Digital audio recordings of the focus groups will be coded/saved with the date of the session and an identification code; no personal identifying information will be placed in the filename or intentionally dictated into the audio recording. Research staff who are responsible for transcribing the interview content will also be responsible for ensuring that identifying information does not appear in the transcript. Once the transcript is completed and checked for accuracy, the audio recording will be erased from the computer.

Should any breaches of participant confidentiality occur, they will be reported to the relevant IRB, DSMB, and PCORI officials.

**12. Describe procedures for reporting Serious Adverse Events (SAEs) and Adverse Events (AEs), and Unanticipated Problems. Include the definition of SAEs and AEs.**

Serious Adverse Events (SAEs) for client participants will be defined as death; a life threatening event such as drug overdose, suicide attempt, or inpatient hospitalization (including substance abuse or psychiatric hospitalizations) due to drug/alcohol overdose, suicidal behavior, or psychiatric distress; or an event that extends an existing hospitalization as defined above. Childbirth, pre-planned elective procedures, and unrelated medical events that require hospitalization will not be considered SAEs. No SAEs are expected as a result of the study procedures or intervention. Client participants in this study are individuals attending therapy in substance abuse treatment, and are thus, as a population, at risk for relapse to substance use or clinical worsening. Although we do not believe the study procedures or intervention places clients at increased risk for clinical worsening, we will review and report events of clinical worsening that lead to a substance abuse or psychiatric hospitalization. These events are not anticipated to occur more often than the baseline rate in this population.

We do not expect and we will not report any Serious Adverse Events for counselor participants, as participating in this study would put them at no related risk for medical or psychiatric distress.

Adverse Events (AEs) for clients will be defined as: report of coercion to participate in the study; significant discomfort from answering research questions or providing urine samples such that the participant decides to stop their participation; risk of harm resulting from a breach of confidentiality; or suicidal thoughts. For client participants, we will also report significant returns to drug/alcohol use defined as a 50% or higher increase of drug/alcohol use compared to baseline, and significant increases in psychiatric symptoms compared to baseline. Clinically insignificant events are not considered AE's. Examples of clinically insignificant events include mild viral illness (e.g., colds, flu, and runny nose), common headaches, minor scratches, and mild symptoms or problems associated with medical conditions not related to drug use (e.g., back pain). Clients in substance abuse treatment often enter treatment with various medical and/or psychological problems which may continue during the course of treatment, and new problems often develop. As per the definition of AEs, only significant worsening of baseline psychiatric or drug/alcohol abuse status or new problems will be reported as AEs.

Adverse Events (AEs) for counselors will be defined as report of coercion to participate in the study; or significant discomfort from answering research questions such that the participant decides to stop their participation.

In prior research, the AEs listed above have been known to occur. However, due to the protections we have put in place we do not anticipate a report of coercion to participate in the study, significant discomfort from answering research questions or providing urine samples, or harm resulting from a breach of confidentiality to occur. Substance abuse and psychiatric disorders are often chronic relapsing diseases, and therefore we anticipate a small percentage of clients will report an increase in drug/alcohol use or psychiatric symptoms during their participation in the study. However, as stated above we will only report these if they are a significant increase from baseline.

All adverse and serious adverse events occurring during the study are documented on a form, reviewed and signed by the PI or Co-I and reported to TRI and other applicable IRBs. All non-fatal

adverse events that meet the above definition of "Severe" are reported to the IRBs within 48 hours of our awareness of the event. Fatal SAEs are reported to the IRBs and relevant PCORI Office within 24 hours of our awareness of the event. A summary of all SAEs and AEs that occurred during the previous year will be included in the annual progress report to the relevant IRBs.

**13. If this study is a chart review, indicate the time frame of data to be collected (from when to when). Also, will the data be collected anonymously (meaning that only aggregate data will be collected, and there will be no names or codes maintained to match the data with the original files)?**

Not Applicable

**14. Children, defined as individuals under the age of 21, must be considered for potential enrollment in every study as subjects unless there are scientific or ethical reasons for excluding them. See below for the permissible exclusionary circumstances listed in the NIH Policy. If no exclusion applies: 1) discuss your plan for the inclusion of children; 2) justify the age range of children to be enrolled; 3) indicate the expertise of the research team with regard to children; 4) describe the facilities for the children; 5) indicate the number of children to be enrolled to give sufficient power for meaningful analysis; 6) describe how the assent process for children 7 to 17 years of age will be carried out.**

